## 2.0 OBJECTIVES

We propose a 3-group, single-blind, parallel design randomized controlled trial in prostate cancer survivors treated with ADT to compare: 1) tai ji quan to 2) strength training and each to 3) a placebo (stretching) control group.

Our specific aims and hypotheses are:

**Primary aim:** To determine and compare the efficacy of tai ji quan training and strength training in reducing the incidence of falls in prostate cancer survivors on ADT.

*Hypothesis:* Tai ji quan and strength training groups will each reduce the incidence of falls compared to a control group. The relative efficacy of each type of training to reduce falls is not yet known.

**Secondary aim:** To determine and compare the efficacy of tai ji quan training and strength training to reduce frailty and dysfunction in prostate cancer survivors on ADT.

*Hypothesis:* Tai ji quan and strength training groups will each reduce the prevalence of frailty and improve physical function compared to a control group. The relative efficacy of each type of training to reduce frailty and improve physical function is not yet known.

**Tertiary aim:** To determine how well the benefits of Tai ji quan and strength interventions persist over a 6-month period.

*Hypothesis:* Group differences in the primary outcome of falls, and secondary outcomes of frailty and physical function will remain for 6 months after the end of the supervised interventions.

**Exploratory Aim:** To explore the patterns and predictors of types of men (including host and treatment factors) who benefit most from tai ji quan and strength training.

**Ancillary study:** We have received supplemental funding to conduct an ancillary study with the following aim: Determine the relationship between mobility characteristics (gait, turning as dynamic balance) during passive monitoring of up to 7 days and ADT exposure, frailty, falls and functioning in up to 130 prostate cancer survivors.

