## 13.0 BIO-STATISTICAL CONSIDERATIONS

### Power and Sample Size

We have powered the sample size based on our primary aim. In older adults, 20%-30% of community-dwelling elders are likely to fall within 1 year [11] and Li and others have reported a reduction in fall risk of 47% from 3 [86] or 6 [41] months of tai ji quan exercise. We are using an effect size for tai ji quan to power for both interventions because we have these data available from our prior work and effects sizes for strength training are similar to tai ji quan [87]. Our study will determine if strength training is as effective as tai ji quan. Using PASS 2008[88], based on a negative binomial regression model [89], at alpha = .05, the variance shared among the dummy vectors representing treatment ( $R^2=.25$ ), and an estimate of the overdispersion parameter (Phi) of 2.5, a sample size of n=300 (n=100 per group) participants will provide 80% power to detect at least a 47% reduction in the fall incidence rate over six months by being in either of the 2 exercise groups versus control. To protect against an estimated attrition of ~17% during the intervention period, 120 participants will be randomized per group (total sample size: N=360). The attrition estimate is conservatively based on the highest attrition rate from our prior strength training trials in prostate cancer survivors (0% and 16% attrition in 6 and 12 month trials, respectively [37, 39]). Though the total # of falls is the primary endpoint, the sample size of N=300 also provides sufficient power to detect differences between experimental and control groups on secondary outcomes of frailty and physical function. We and others' have data on the effect of exercise on individual components of frailty in prostate cancer survivors on ADT and self-report physical function. With a sample of N=100 per group we have a sufficient sample to detect a difference in 2.5% of lean body mass [90, 91], a 4 sec. faster chair stand time [37, 91], a 1.1 sec. faster gait speed [91], and a 9% difference in self-report physical function scores [37].

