Aim 1: Compare the relative efficacy of tai ji quan and strength training to prevent falls: We will determine the efficacy of tai ji quan and strength training by comparing each of them to the control condition while adjusting for important covariates using negative binomial regression models which will analyze total number of falls per participant that occur from baseline to 6 months. A negative binomial regression was chosen over a Poisson regression for modeling the count data because of the overdispersion that is common with actual research data. [88, 93] Intervention type will be entered into the model as 2 dummy variables, with the reference group being the control group. This will allow a comparison of the each of the intervention groups against control. A *second* model will be run with strength training as the reference category to compare the intervention groups to each other. In addition to standard ITT analysis, the impact of participants who drop out of the study on the falls outcome will be examined in a secondary data analysis. A significant incidence rate ratio (IRR) less than 1.0 for the dummy vector representing tai ji quan and/or strength training would provide support for the hypothesis that the respective intervention reduced the rate of falls compared to the control group.

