Aim 2: To determine and compare the efficacy of tai ji quan training and strength training to reduce frailty and dysfunction: Each participant will be classified as frail, pre-frail or robust based on his total frailty score (see **Measures**). We hypothesize that the number of men classified as frail or pre-frail will decrease over the course of the study in the tai ji quan and strength training groups compared to control. Formal tests of frailty hypotheses will be conducted in a generalized mixed effects modeling framework as implemented in the R statistical computing environment. [94] Frailty category will be the multinomial dependent variable (with “robust” as the reference group) and study time point (0, 3 and 6 mos.), group (control as the reference group) and the group x time interactions will serve as predictors. [95] We will also run a second model with strength training as the group reference category to compare the two experimental groups to each other. Significant group x time interactions will indicate that the distribution of frailty between the groups (e.g., tai ji quan vs. control) is different across time. For significant interactions, additional contrasts testing for frailty differences will be examined to describe the pattern of change across time. Group differences across time in the continuous physical function and individual frailty measures will be tested in a linear mixed effects modeling framework [94] to estimate the trajectory of change in each dependent variable across time for each individual in each group, and then comparing the average trajectories across groups. The primary effect of interest is a cross-level interaction. Specific hypotheses about treatment group effects will be specified by adding dummy variables and hypotheses will be tested through group x time interactions (as above). We will also evaluate the practical significance of the interventions by summarizing results with respect to effect size.

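### The plan says the trial will determine whether strength training is as effective as tai ji quan, but a difference test with no margin cannot establish this, and a non-significant result could be misread as equal efficacy

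*Combined protocol and SAP*

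**What the plan says.** The sample-size text in section 13.0 takes one effect size, from tai ji quan trials, for both exercise arms, on the ground that "effects sizes for strength training are similar to tai ji quan". The next sentence reads: "Our study will determine if strength training is as effective as tai ji quan". The power statement then covers comparisons with control only: 300 evaluable men, 100 per group, give "80% power to detect at least a 47% reduction in the fall incidence rate over six months by being in either of the 2 exercise" arms against control.

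In the Aim 1 analysis, control is the reference group. A second "model will be run with strength training as the reference category to compare the intervention groups to each other". The one decision rule there is that a significant IRR below 1.0 "would provide support for the hypothesis that the respective intervention reduced the rate of falls compared to the control group". Nothing comparable is given for the contrast between the two exercise arms. Aim 2 repeats the device for frailty ("We will also run a second model with strength training as the group reference category to compare the two experimental groups to each other"), and Aim 3 carries the same modelling strategies into follow-up.

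Section 2.0 makes comparing the two programmes part of the primary aim but states no direction for it: "The relative efficacy of each type of training to reduce falls is not yet known".

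**The concern.** To show that one treatment is as effective as another, a plan needs a stated largest acceptable difference and a rule that checks whether the CI excludes anything worse. A test of IRR = 1 can show that the arms differ. It cannot show that they do not.

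The gap matters because the plan expects the two effects to be similar. A non-significant head-to-head IRR is then the outcome to expect, and the plan does not say how to read it. The only sentence that gives it a meaning is the one about being as effective. What is at stake is one conclusion within the primary aim: whether the two programmes could be presented as interchangeable on the strength of an interval wide enough to hide a sizeable difference.

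**Working it through.** **Inputs from section 13.0:** alpha 0.05 (sidedness not stated), 80% power, IRR 0.53, overdispersion 2.5, R² 0.25, 100 evaluable per group. **Not given:** the control fall rate over six months, and any margin.

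**1. The plan's own figure.** The cited Poisson-regression formula, inflated for overdispersion, is

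N = φ(z_α√V0 + z_β√V1)² / [λ0 (ln IRR)² (1 − R²)],

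with V0 = 1/(1−p) + 1/p and V1 = 1/(1−p) + 1/(0.53p), where λ0 is the control rate per person over six months and p is the share of men in the exercise arm.

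- With two-sided alpha, p = 1/2 and an assumed λ0 = 1.0: 2.5 × (1.960 × 2 + 0.842 × 2.403)² / (0.403 × 0.75) ≈ 292.
- N = 300 needs λ0 of about 0.97 (p = 1/2) to 1.13 (p = 1/3).
- If the quoted 20–30% of elders falling per year is taken as 0.10–0.15 falls per person per six months (an assumption), the formula gives about 1,950 to 3,400.

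The stated N therefore cannot be reproduced without the missing rate. Below, the stated 80% power is taken as true, which favours the plan.

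**2. Precision implied by the stated power.**

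- Exercise against control: SE(ln IRR) = |ln 0.53| / (1.960 + 0.842) = 0.635 / 2.802 = 0.227. A one-sided alpha would imply a larger SE, 0.635 / (1.645 + 0.842) = 0.255, so the two-sided reading is the kinder one.
- Strength training against tai ji quan: if both arms achieve the planned 47% reduction, this contrast has fewer falls in it. With variance proportional to the mean, the SE grows by √[(2/0.53) / (1 + 1/0.53)] = 1.14, to 0.259.

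The range for the head-to-head SE is therefore 0.227 to 0.259.

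**3. What the difference test delivers.** The 95% CI at an observed IRR of 1.0 is exp(±1.96 SE). The chance of non-significance at a true IRR θ is 1 − Φ(d − 1.96) − Φ(−d − 1.96), with d = ln θ / SE and the SE held fixed.

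| | SE 0.227 | SE 0.259 |
|---|---|---|
| 95% CI at IRR 1.0 | 0.64–1.56 | 0.60–1.66 |
| Non-significant, true IRR 1.25 | 83% | 86% |
| Non-significant, true IRR 1.33 | 76% | 80% |
| Non-significant, true IRR 1.50 | 57% | 65% |
| True IRR with 80% power | 1.89 (or 0.53) | 2.07 (or 0.48) |

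**4. What a margin would require.** The documents give none, so these margins are illustrations only. Non-inferiority power at 100 per arm, one-sided 0.025, true IRR 1, is Φ(ln m / SE − 1.96).

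| Assumed margin m | Power | Evaluable n per arm for 80% |
|---|---|---|
| 1.25 | 14–17% | 810–1,059 |
| 1.50 | 35–43% | 246–321 |
| 2.00 | 76–86% | 84–110 |

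**5. If falls are rarer.** Directly from the overdispersion figure, SE = √[2 × 2.5 / (100 × mean)]. At assumed active-arm means of 1.0 and 0.3 falls per six months, the CI factor is 1.55 and 2.23. With the 47% reduction, a mean of 1.0 implies 1/0.53 ≈ 1.9 falls per control participant in six months.

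**The case against.** The disputed claim is one informal sentence. It follows the explanation for borrowing the tai ji quan effect size, and can be read as admitting that the borrowed figure is untested for strength training. The formal statements (the background, the objectives, the design summary and the Aim 1 heading) describe an open comparison of relative efficacy. A re-referenced negative binomial model is a proper way to make such a comparison.

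A reader might go further and infer that the sponsor plans to declare the programmes equal if the head-to-head test is non-significant. The documents do not support that. No section says how such a result will be read, and the only decision rule concerns a significant reduction against control.

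It is also fair to say that the plan defines no material difference between the arms. The excesses of 25%, 33% and 50% are illustrations, and the test does reach 80% power at an IRR of about 1.9 to 2.1.

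All of this stands, and it limits the point to a risk of misreading. It does not rescue the sentence, which promises without qualification something that the design cannot supply. The neutral wording in section 2.0 is a reason to bring the sentence into line with it.

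**Conclusion.** The point holds as a mismatch between a stated property and the design. There is no margin, CI criterion, power or decision rule for strength training against tai ji quan, so the trial can estimate that contrast but is not set up to show that one programme is as effective as the other. An observed IRR of 1.0 would remain compatible with roughly 36–40% fewer to 56–66% more falls in one arm. Only a very wide margin, near 2.0, would approach or exceed 80% non-inferiority power at 100 per arm.

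These figures assume that the stated power is correct, a two-sided alpha, 100 evaluable men per arm and, for the wider end, a 47% reduction in both exercise arms with variance proportional to the mean. No gain from covariate adjustment is counted. If the fall rate is below what the power claim needs, the intervals are wider.

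The comparisons with control are not affected by this point, and the neutral comparison in section 2.0 is sound as worded.

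**What to change.** In section 13.0 (Power and Sample Size), replace the sentence with: *The study will estimate the strength training versus tai ji quan IRR with its 95% CI; the sample size is not set to establish equivalence or non-inferiority.*

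In the Aim 1 analysis, after the second model, add: *This contrast will be interpreted from the IRR and its 95% CI; a non-significant difference will not be reported as equal efficacy.*

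Do not write a fixed CI width into the plan, because the widths above depend on a power claim whose fall rate is not stated. If the sponsor wants to keep the stronger claim, the alternative is to pre-specify and justify a margin and report the power for it. The second table shows how demanding that would be.

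The rewording needs no new data, no change of sample size and no change of model. Its cost is that the stated claim becomes less favourable.

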**Protocol Revision Dates:**

[10/25/2018](#)

- *Added description of participant incentives (2.0)*
- *Clarified Inclusion Criteria language regarding other treatment (5.0)*
- *Edited Exclusion Criteria language regarding exercise—made it more specific (5.0)*
- *Update language regarding OSCaR recruitment process (10.a)*

[01/09/2019](#)

- *Updated eligibility (removed aerobic exercise; clarified strength training criteria; added criteria about movement and neurological disorders)*
- *Updated randomization stratifications*
- *Added information about electronic consent*
- *Adding performance testing measures*
- *Adding questionnaires*
- *Added details about compensation and how we'll pro-rate*

[02/22/2019](#)

- Added FACIT-Fatigue to outcome measures (p. 9) and the Schedule of Events table

[03/01/2019](#)

- Added chair sit in reach to Secondary Endpoint: Physical Function (p. 10) and the Schedule of Events table

[04/26/2019](#)

- Update recruitment language to include sources such as Cohort Discovery, Research Data Warehouse, MyChart, Tuality, Adventist, etc. (section 10.a and 14.0)
- Updated eligibility inclusion/exclusion criteria (section 5.0)
- Clarified language for Adverse Event tracking and reporting (section 19.1 and 19.2)
- Updated scheduled of events for Managing Side Effects of ADT- MSQ (removed it at 3-months) (section 8.0)
- Replaced “School of Nursing” with “Knight Cancer Research Building” throughout the document

[05/22/2019](#)

- Add title to first page, per KCI audit request
- Edit Participant Incentives under section 3.0 (made the pro-rating system simpler and more inclusive)

[2/5/2020](#)

- Added further clarification and refinement of Adverse Event reporting
- Added clarification of inclusion criteria related to class attendance

[4/3/2020](#)

- 3.0 Study Design Methodology- added remote delivery of exercise classes
- 3.0 Study Design Methodology- added remote delivery of testing (and potential skipped/delayed visits)
- 7.0 Setting- Added “remote delivery” as possible setting
- 8.0 Schedule of Events- added remote testing assessments to table
- 10.0 Risks to Subjects- added remote safety considerations

[5/21/2020](#)

- 8.0 Study Procedures and Schedule of Events- Added boilerplate language for use of MyChart for recruitment
- 8.0 Study Procedures and Schedule of Events- Added 3M TUG as follow-up assessment completed during remote testing
- 7.0 Setting- Removed language related to recording classes

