Strength Training: Recommendations for improving muscle strength in older adults support the use of multiple-joint exercises for 1-3 sets per exercise at a weight that can be lifted 8-12 times [32]. Our strength training intervention uses weighted vests to apply resistance during lower body exercise - an innovative and safe method to maximize the effect of exercise on lower body musculoskeletal function. The strength training program used in this study is based on training programs that improved neuromuscular function (strength, gait, and balance) and reduced fall risk factors in our prior studies in women with [33, 34] or without cancer [35, 36] and in our recently completed trials in prostate cancer survivors on ADT [37-39]. Participants wear a weighted vest while performing exercises using functional movement patterns that challenge balance by using muscle groups and movement involved in everyday activities (chair rises, 90° squats, side-to-side squats, toe raises, lunges (forward, lateral, backward, walking), multi-directional step ups). The vest has multiple small pockets that each holds a ½-lb weight, so that the intensity of the exercise can be adjusted slowly. Pockets are distributed evenly around the torso in order to add resistance in an ergonomically efficient and safe way. Weighted vests allow men to perform functional exercises without safety risks related to balance disruption that can occur with handheld barbells and dumbbells.

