Tai ji quan: The protocol contains an integrated exercise routine consisting of 8 purposeful movement forms and a set of therapeutic movements. This program was vigorously evaluated in 2 trials by Li et al [40, 41], and subsequently in community settings [42] and with a clinical population [43]. Because the goal of the exercise is to assist patients in retaining postural control and stability, the protocol is specifically designed to challenge limits of stability and train gait patterns, as reflected in movements such as upright trunk positioning, displacement of body's center of mass over the weight-bearing leg, and step initiation, locomotion, and termination. The only resistance applied during tai ji quan will be the participant's own body weight. The early stage of the program (i.e., the first 12 weeks) emphasizes primarily learning and practicing single forms with multiple repetitions. The later stage focuses on performing individual forms to improve postural balance and movement locomotion and reviewing and practicing forms learned in previous sessions.

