**Stretching Control:** Participants in the control group will attend a supervised flexibility program of the same total weekly duration as the experimental arms (e.g., 3, 60-min sessions per week). Control participants will perform a series of whole body stretching exercises, according to the ACSM guidelines for flexibility training [32], with a focus on developing and maintaining a healthy back. Stretching exercises will be performed in a seated or lying position that minimizes weight-bearing forces that might increase fitness or mobility. Many exercise trials in older adults, including ours, have used a stretching control condition and have shown no effect of this training on muscle strength [44]. Since the ACSM recommends “avoidance of inactivity” among cancer survivors to optimize quality of life [30] the increases in range of motion and sense of well-being from stretching may be viewed as a benefit for participants in this group. Men in this group will be asked to refrain from initiating new strength training or tai ji quan programs during their time in the study. Our prior exercise trial in prostate cancer survivors on ADT had a similar stretching control group and retention and compliance rates were similar as men in the strength training group [38]. In contrast, in our recent trial of partnered exercise in prostate cancer survivors and spouses, couples assigned to a usual care control group had greater attrition (25%) compared to the exercise group (0%); thus, the use of a placebo control group is an important feature of this study’s retention plan.

Participants will perform all exercise sessions remotely (e.g., at home) using videoconferencing software. The necessary exercise equipment and a webcam may be provided if needed, and will be returned at the end of study. Participants will receive written and verbal instructions for installing and using videoconferencing software. During these web-based, group video conferences, the exercise instructors will observe and instruct participants using the same format as on-site classes.

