## **7.0 SETTING**

The primary testing site will be at the Oregon Health & Science University (OHSU) Knight Cancer Research Building while exercise training will be offered at OHSU and several community sites serving different geographic regions of the Willamette Valley. Study visits and exercise training may also be delivered remotely via video conferencing. Conferences are set up by a private link sent to participants by email. Any data recorded during training or study visits will be entered directly into databases on staff computers.

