Interested participants will be screened either by phone or in person using an IRB approved screening script. After initial screening, potentially eligible men will be scheduled for consent and baseline screening and possible further baseline testing in qualified men. Screening includes review of fall history in the past year, a 3-meter Timed Up and Go walk at usual pace, and standing up and down from a chair five times as fast as safely possible. The testing session will include DXA, performance testing and survey completion and will be repeated at 3- and 6-mos. (post-intervention), and 6 mos. after completion of the intervention (follow-up). Total time for performance testing and survey completion is ~2-2.5 hours. Men will complete written surveys on a computer at baseline and online for follow-up visits, unless they prefer to complete paper surveys. Staff will review surveys for completeness and follow up with participants in person or by phone on missing data. To reduce bias we will retain blinding of the research assistants who conduct the testing visits, by having the Project Director provide each participant with an envelope that contains his random group assignment *after* baseline testing is complete. Qualified men will

be randomly assigned to 1 of 3 groups: 1) tai ji quan, 2) strength training or 3) stretching control. To avoid confounding and differential tolerance to exercise by ADT history and age, block randomization stratifying for timing of ADT (past or current) and will be done using EXCEL to generate random assignments from each block. Assignment will be in random blocks of 6 to 9 within each wave (~42-48 men) to facilitate even enrollment and to prevent the Project Director from predicting group assignment.

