During remote exercise and testing sessions, additional safety precautions will include: 1) Providing safety recommendations specific to exercises and/or assessments (i.e., standing near a wall for balance activities) 2) Adapting the exercise protocol as necessary (ie. limit weight.) 3) Verifying address of remote exercise location (i.e., home address), should the exercise instructor or Research Assistant need to call 911 in an emergency 4) Ensuring that emergency contact information is up-to-date and readily available.

Ancillary study: Participants in the ancillary study incur no risk from exercise.

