All analyses will retain each participant in the group he was randomly assigned regardless of missing data or drop out status (i.e., intention to treat). We will track medical treatment changes and disease progression during the study to describe the sample or justify why participants exited the study. In the unlikely event of a large subgroup, these data could be used for exploratory subgroup analysis to suggest directions for future research. Age, timing of ADT (current vs. past), fall history at enrollment and baseline frailty will be considered as possible covariates in all analyses. Age and timing of ADT (past vs current) are included since they may affect exercise tolerance and/or responsiveness to exercise training; fall history is included because we want to examine the efficacy of the interventions to reduce falls in men with a fall history and prevent falls

among men who have not recently fallen. Analyses will be conducted in Stata, R, and/or Mplus statistical software packages. Full information maximum likelihood estimation (FIMLE) will be used to estimate the models, as appropriate, because it is less biased and more efficient than other techniques for handling missing or incomplete data[92].

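### Men are randomised by wave and ADT timing, but no Aim 1–3 model commits to either term; delivery mode is described inconsistently and has no planned summary

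*Combined protocol and SAP*

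**What the plan says.** **Randomisation.** Section 8.0 (Screening tests and procedures) stratifies by past or current ADT and adds: "Assignment will be in random blocks of 6 to 9 within each wave (~42-48 men". Section 14.0 plans 8 waves of 45 men, 15 per class. Section 3.0 (Study Arms) has all three programs running at each exercise location in each wave. The Section 12.0 timeline marks waves 2, 4 and 8 as regional-site waves.

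**Analysis.** Section 13.0 says "Age, timing of ADT (current vs. past), fall history at enrollment and baseline frailty will be considered as possible covariates in all analyses". The Aim 1 paragraph adjusts for important covariates without listing them. The Aim 2 and Aim 3 paragraphs add neither wave nor delivery mode.

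**Delivery mode.** The 4/3/2020 entry in the revision list reads "3.0 Study Design Methodology- added remote delivery of exercise classes". In the current text, Section 3.0 states: "Participants will perform all exercise sessions remotely (e.g., at home) using videoconferencing software". Section 7.0 offers training at OHSU and community sites and then says: "Study visits and exercise training may also be delivered remotely via video conferencing". No section says who sets the mode, when, or whether it is the same for all arms in a wave.

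**Adaptation at home.** For remote exercise and testing, Section 10.0 lists, among other precautions, "Adapting the exercise protocol as necessary (ie. limit weight". For strength training, Section 3.0 says "Participants wear a weighted vest while performing exercises using functional movement patterns"; for tai ji quan, "The only resistance applied during tai ji quan will be the participant's own body weight". Control stretching is seated or lying.

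**The concern.** Two things are left open.

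First, the analysis does not match the randomisation. Waves differ in calendar time, site and probably delivery mode, so fall rates may differ between them. A model that ignores wave leaves that variation in the error. Calling ADT timing only a possible covariate also leaves a modelling choice open until the data are seen.

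Second, the head-to-head comparison is part of the primary aim, and Section 13.0 says the study will settle whether strength training is as effective as tai ji quan. If home delivery weakened one program more than the other, the pooled contrast would be an average over modes. A reader would need the by-mode figures to interpret it, and none are planned. Section 3.0 does provide for testing men both in person and remotely to check remote testing visits; nothing similar is planned for remote training.

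**Working it through.** **1. The plan's own structure.** 8 × 45 = 360 men; 45 / 3 = 15 per arm per wave; 8 × 15 = 120 per arm. With attrition of one sixth (the plan says about 17%), 120 × 5/6 = 100 evaluable per arm, as stated. The 80% power claim for N=300 cannot be reproduced because no control fall rate is given, but this point does not depend on it.

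**2. Does omitting wave or mode bias the arm contrasts?** Let m be the control mean on site, p the share of men at home (equal in all arms when mode is set by wave), and d the rate ratio of home to on-site delivery, common to all arms. Take the plan's IRR of 0.53.
- Control mean: m[(1−p) + pd]
- Exercise mean: 0.53 m[(1−p) + pd]
- Ratio: 0.53 for every p and d. For example, with p=0.5 and d=1.3: 0.53 × 1.15 / 1.15 = 0.53.

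Simulation agrees (8 waves × 3 arms × 15 men, control mean 1.0, dispersion 2.5, 6 of 8 waves remote, 1,000 runs per setting, d = 0.7, 1.3 or 2.0). Without mode in the model, the IRR is 0.53 for tai ji quan and 0.52–0.54 for strength. With mode, it is 0.53 and 0.52–0.53.

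**3. What do wave and ADT timing buy?** Simulated stratified blocks of 6 and 9, 300 men, 8 waves. Assumed: mean 0.6 falls, current/past ADT rate ratio 1.5, dispersion 1.5. Model SE of the arm effect without and then with both terms:
- wave log-rate SD 0.2: 0.258 → 0.253, a cut of 1 − 0.253/0.258 = 1.9%
- SD 0.4: 0.260 → 0.251, a cut of 3.5%
- SD 0.6: 0.268 → 0.253, a cut of 5.6%

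A repeat gave cuts of about 2–5% at dispersion 1.5 and 1–3% at 2.5 (the plan's overdispersion figure), with no change in the IRR. The overall range is about 1–6%.

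**4. What if home delivery weakens only strength training?** With equal control rates in both modes and home strength IRR h, the pooled strength IRR is (1−p) × 0.53 + p × h. Dividing by 0.53 gives strength versus tai ji quan.
- h = 0.70, 5 of 8 waves remote: (3 × 0.53 + 5 × 0.70)/8 = 0.636; 0.636/0.53 = 1.20.
- Half the log effect lost, h = √0.53 = 0.728: 1.09, 1.19, 1.28 and 1.37 for p = 0.25, 0.50, 0.75 and 1.
- All lost, h = 1: 1.22 to 1.89 over the same range of p.

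A main effect for mode does not separate this. With 6 of 8 waves remote, the simulated head-to-head IRR is 1.28 with or without mode at half loss, and moves only from 1.65 to 1.63 at full loss. Only arm effects by mode show it.

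**5. Power for arm by mode.** Take half loss, 2 on-site waves (30 per arm) and 6 remote (90 per arm), no attrition, control mean 1.0 and dispersion 2.5. The variance of a cell's log mean is (1/μ + 2.5)/n. For strength versus tai ji quan, home minus on site: 2 × (1/0.53 + 2.5)/30 + (1/0.728 + 2.5)/90 + (1/0.53 + 2.5)/90 = 0.292 + 0.043 + 0.049 = 0.384, so SE = 0.62. The difference is 0.5 × |ln 0.53| = 0.317, and z = 0.51. Two-sided 5% power is P(Z > 1.45) + P(Z < −2.47) ≈ 0.08.

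**The case against.** **The precision gain is minor, and ADT timing is already named.** This is right as to size. Leaving out randomisation strata also tends to make standard errors too large rather than too small. What stands against it is that wave is named nowhere, ADT timing is optional, and the Aim 1 covariates are not listed.

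**A reader might infer that, with wave and mode in no model, a delivery effect could pass for a difference between modalities.** The documents do not support this. Randomisation within wave, with all three programs at each location, balances wave-level delivery across arms; step 2 shows a common effect cancels. Nor would a wave or mode main effect recover a loss confined to one arm (step 4).

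**A reader might infer that the weight allowance makes strength training the weaker program at home.** Section 10.0 allows adaptation as necessary; it does not plan a reduction. Section 3.0 says equipment may be provided and the class format is the same. Section 10.0 also gives standing near a wall during balance activities as an example, which could equally touch tai ji quan. The weight example bears on the vest-loaded arm, but its size and direction are unknown.

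**A reader might infer that men chose their mode after assignment.** No section says so. The documents are silent on the rule, which is a reason to record it and not evidence of imbalance.

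**The pooled contrast of programs as delivered is a legitimate target.** This stands. An analysis with about 8% power cannot justify restricting the head-to-head claim.

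**Conclusion.** The analysis should follow the randomisation, and at present it does not commit to doing so. The consequence is modest: a standard error of the arm effect about 1–6% larger than necessary, under assumed wave variation, ADT effect and dispersion. The arm contrasts are not biased, provided mode was common to all arms within a wave. (For the multinomial frailty model this means no confounding; logit coefficients shift somewhat when any prognostic term is added.)

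The conflict between Sections 3.0 and 7.0 on delivery mode is plain on the page and must be reconciled. A difference in arm effect by mode is possible but unquantified: the documents give neither the share of men trained at home nor the extent of any adaptation. The head-to-head IRR of 1.20, like the other values in step 4, illustrates its own assumed inputs and is not an estimate. It supports an exploratory by-mode report and no limit on the primary conclusion.

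**What to change.** 1. In Section 13.0, replace the optional wording for ADT timing with a fixed term, and add wave (8 levels, fixed or random intercept), in every Aim 1–3 model. Confirm the full list of stratification factors: the Section 8.0 sentence is incomplete in the text available, and its rationale also mentions age. Cost: seven wave coefficients, or one variance, plus one for ADT timing.
2. Reconcile Sections 3.0 and 7.0 on delivery mode. Document, for each wave, how and when mode was set, whether it was the same for all arms, and whether it changed during the intervention. The 9/12/2024 revision already refers to baseline data on 284 men, so for most or all waves this means recovering a record. The documents do not say that mode was recorded, so some effort may be needed.
3. Add, labelled exploratory, the Aim 1 contrasts by delivery mode: arm-by-mode estimates with confidence intervals, limited to waves where mode was common to all arms, with low power stated. Waves that changed mode need their own category. Use the results to inform interpretation of tai ji quan versus strength training.
4. Keep the pooled intention-to-treat contrast as primary.

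Items 1, 3 and 4 need only plan wording before the analysis; no clinical procedure changes.
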